2. STUDY OBJECTIVES

Primary objectives

1. To be the first attempt to validate the prognostic potential of early recording [between 24-36 hours post ROSC] of P25/30 potentials in comatose survivors who are admitted to a British ICU after out of hospital cardiac arrest and who are not treated hypothermic targeted temperature management.
2. To assess the Specificity, the Sensitivity, the Positive and Negative Predictive Value of the early [between 24-36 hours post ROSC] P25/30 SSEPs recording in predicting poor neurological outcome after out of hospital cardiac arrest.

Secondary Objectives

1. To test the potential prognostic superiority of early P25/30 SSEPs recording against the early N20 SSEP recording in predicting poor neurologic outcome in the same cohort of patients.
2. To test if P25/30 SSEPs are associated with higher sensitivity and negative predictive value than N20 and subsequently to test if that superiority of P25/30 is consistently associated with greater accuracy in the early detection of poor neurologic outcome [especially among those patients with unilaterally or bilaterally present N20 SSEPs].
3. Add further knowledge regarding the prognostication significance of SSEP and specifically of P25/30 potentials in comatose survivors post out of hospital cardiac arrest who are treated in ICU. Provide reliable prospective evidence of the accuracy and reproducibility of the P25/30 signal recording.

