Interpretation of the SSEP recording for study purposes in details

Cortical N20 response is to be described as bilaterally absent (which is a good predictor of poor neurological outcome), or in other cases it may be present on one or both sides.

If the cortical N20 response is absent, the presence of the peripheral N9 and N13 response must be present to ensure that the response has arrived at the cortex. Cervical lesions need to be excluded if Cortical N20 response is absent.

The results of the SSEP from the patients enrolled to the study will be additionally interpreted for the presence or absence of the P25/30 waveforms. The additional interpretation for the study purposes will be as follows:

1. Check that baseline is clear and stable.
2. Check that all measured components are reproducible (should be possible to superimpose waves)
3. Check that peripheral nerve (N9) potential is present
4. Check that cervical spinal (N13) potential is present
5. Check that scalp (N20) potential is present and higher than 0.5 microvolts.
6. Check that scalp (P25/30) potential is present and higher than 0.5 microvolts..
7. As the P25/30 potential could be generated in the absence of N20 as they come from two distinct areas of the brain cortex, the presence of either the P25/30 or the N20 would be confirmed when the amplitude of each one is equal or higher than the amplitude threshold [0.5 microvolts] used for the analysis of the SSEPs. The presence and the amplitude of P25/30 will not be dependent on the presence of N20 in the same recording as each one of them can exist in the absence of the other
8. Measurement of the amplitude of recorded P25/30 and N20 and their combinations. Test if there is a correlation of the recorded amplitudes and their ratio [P25/30 to N20] with the positive predictive value of N20 for the favourable neurological outcome.

Explanation clarification between the usual Derriford ICU post cardiac arrest care and what additionally will be done for the research study purposes

[figure not shown]

Figure 3. Explanation-clarification of the usual Derriford ICU post cardiac arrest care and what additionally will be done for the research study purposes

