7. STATISTICS AND DATA ANALYSIS

7.1 DESCRIPTION OF STATISTICAL METHODS

Demographic information of participants will be summarized using descriptive statistics and presented in tables to provide an exploratory overview of the study population.

Continuous measures will be summarised as means, standard deviations and ranges where the distribution appears normal, and as medians, inter-quartile ranges and ranges otherwise.

Categorical data will be summarised by frequencies and percentages.

The primary outcome measure is the CPC score at hospital discharge with discrete values ranging from 1 to 5. The score will be dichotomised as 1-2 (positive or good outcome) and 3-5 (negative or poor outcome).

Sensitivity, specificity and predictive values of P25/30 in predicting poor outcome will be computed and the results compared to that of N20. Where appropriate, parameter estimates will be presented with 95% confidence intervals. Significant demographic and clinical predictors of poor neurological outcomes will be assessed and identified using regression models.

Statistical data analysis will be undertaken once data collection from the required number of participants is completed. No interim analysis is scheduled for this study.

Analyses will be performed in SPSS version 24 (or later), supplemented where required by Stata SE version 14.2 (or later) and R.

a. THE NUMBER OF PARTICIPANTS

Sample size calculation was based on diagnostic test accuracy (adequate sensitivity) of P25/30. A previous study (Kim et al. 2018) on patients treated by hypothermic targeted temperature management showed that the sensitivity of P25/30 in predicting poor outcome is 90.12% (95% CI, 81.5–95.6%). Though the proposed study will be based on those who are not treated by hypothermic targeted temperature management, the result (90%) is the 'best' available information regarding pre-determined sensitivity of P25/30. From experience of the team and analysis of the past three-years

pilot data, the prevalence of poor outcome was assumed to be 75%. In order the maximum marginal error of estimate does not exceed from 5% with 95% confidence level, and adjusting for drop-out/lack of consent at 3%, the minimum required sample size will be 115. No power was assumed in the calculation of the sample size as there is no testing of hypothesis.

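### The planned correlation of SSEP amplitudes and their ratio with the positive predictive value of N20 does not exist as written and should become an exploratory patient-level analysis

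*Combined protocol and SAP*

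**What the plan says.** Protocol section 4.1, under the detailed interpretation of the recording for study purposes, lists eight steps. Item 8 has two sentences. The first asks for the amplitudes of P25/30 and N20 to be measured. The second plans an analysis: "Test if there is a correlation of the recorded amplitudes and their ratio [P25/30 to N20] with the positive predictive value of N20"; it goes on to specify that this is the value for the favourable outcome. Item 7 sets presence at 0.5 microvolts or more for each potential and adds that "each one of them can exist in the absence of the other".

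Elsewhere accuracy is framed for poor outcome:
- Section 2, primary objective 2, concerns "P25/30 SSEPs recording in predicting poor neurological outcome after out of hospital cardiac arrest".
- Section 2, secondary objective 1, compares with "early N20 SSEP recording in predicting poor neurologic outcome in the same cohort of patients", and secondary objective 2 asks whether P25/30 has "higher sensitivity and negative predictive value than N20".
- Section 7.1 states: "Sensitivity, specificity and predictive values of P25/30 in predicting poor outcome will be computed and the results compared to that of N20".

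Section 7.1 describes no analysis of amplitude or ratio. It gives no rule for combining left and right sides, no amplitude strata, and no rule for a potential that is absent.

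**The concern.** A correlation needs two quantities that both vary over the same units. Amplitude and the P25/30:N20 ratio have one value per patient (or per side). A predictive value has one value per cohort. Taken at its word, item 8 pairs a variable with a constant.

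The label adds a second difficulty. If absence of the potential is the positive test and poor outcome is the target, as in sections 2 and 7.1, the quantity in item 8 is a negative predictive value. The same number would then carry opposite names in two parts of one plan.

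What is at stake is prespecification of a secondary question: whether signal size adds information once N20 is known to be present. As the text stands, someone must later choose the model, the population, the handling of absent P25/30 and the rule for two sides. Section 7.6 makes a separate SAP optional, so nothing guarantees that these choices precede sight of the data.

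**Working it through.** The plan gives no figure for this analysis, so there is none to reproduce. The check is one of definition, followed by an illustration of what a computable version could deliver.

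**1. The correlation.** For patient i let A_i be the amplitude or ratio, and let P be the predictive value of N20. P is the same for every i, so cov(A, P) = 0 and var(P) = 0. The coefficient is r = cov(A, P) / [sd(A) × sd(P)] = 0/0, which is undefined. Ranking does not help, because all values of P are tied.

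**2. The label.** Section 4.1 says: "Cortical N20 response is to be described as bilaterally absent (which is a good predictor of poor neurological outcome". With bilateral absence as the positive test and poor outcome as the target, a negative test means N20 present on at least one side. Then

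NPV of absent N20 for poor outcome = P(good | N20 present) = PPV of present N20 for good outcome.

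The two names describe one number.

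**3. Patients available.** Inputs from section 7.1: 115 participants, 3% loss, 75% poor outcome, P25/30 sensitivity 90%.
- Evaluable: 115 × 0.97 = 111.6, about 112.
- Poor: 112 × 0.75 = 84. Good: 112 − 84 = 28.

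Assumptions not in the documents: N20 sensitivity for poor outcome of 40 to 60%, and N20 present in all 28 good-outcome patients.
- Poor with N20 present: 84 × 0.60 = 50 down to 84 × 0.40 = 34.
- N20-present group: 78 down to 62 patients.
- P(good | N20 present): 28/78 = 0.36 to 28/62 = 0.45.

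**4. Precision in the N20-present group.** Hanley-McNeil variance for an AUC A with n1 index and n2 comparison patients:

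var = [A(1−A) + (n1−1)(Q1−A²) + (n2−1)(Q2−A²)] / (n1 × n2), with Q1 = A/(2−A) and Q2 = 2A²/(1+A).

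At A = 0.75, Q1 = 0.600, Q2 = 0.643 and A² = 0.5625. The formula is not symmetric in the two groups, so both orientations are shown as 95% half-widths (1.96 × SE).

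| Poor / good | Poor as index | Good as index |
|---|---|---|
| 34 / 28 | 0.120 | 0.125 |
| 42 / 28 | 0.113 | 0.121 |
| 50 / 28 | 0.107 | 0.119 |

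**5. The ratio and log amplitude.** At 90% sensitivity, poor-outcome patients with P25/30 present number 84 × 0.10 = 8.4, about 8. Those who also have N20 present cannot exceed that. So among N20-present poor-outcome patients, at least about 34 − 8 = 26 of 34, or 50 − 8 = 42 of 50, have no measurable P25/30. A model using the logarithm of P25/30 amplitude would lose them. A ratio analysis needing both potentials has at most about 8 poor and 28 good outcomes. The AUC half-width at 0.75 is then 0.212 with poor as index and 0.174 with good as index.

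**The case against.** The protocol uses correlation loosely for association; section 3, for example, speaks of correlating P25/30 with prognosis. On that usage item 8 asks whether the chance of a good outcome given N20 present changes with amplitude, and that can be computed by strata or regression. This stands for the underlying question, but the text defines neither strata nor a model. The only threshold given, 0.5 microvolts, already defines presence and so cannot divide patients whose N20 is present.

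A reader might infer that item 8 contradicts the outcome direction of the rest of the plan. It does not do so numerically. It names its own target ("with the positive predictive value of N20 for the favourable neurological outcome"), the quantity equals the negative predictive value for poor outcome, and section 1.1 shows interest in what present potentials predict. Only the naming needs aligning.

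A reader might also infer that the ratio fails generally because P25/30 can occur without N20. Conditioning on N20 present removes most of that problem, since the denominator is then at least 0.5 microvolts on the side concerned. The larger difficulty is the opposite case, N20 present with P25/30 absent.

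Finally, amplitude could be taken for the central question of the study. The documents do not support that. Amplitude and ratio appear in no objective, endpoint or statistical method; the stated questions concern presence or absence of P25/30.

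**Conclusion.** The second sentence of item 8 cannot be carried out as worded, and section 7.1 offers no substitute. That conclusion needs no numerical assumption. The relabelling is a matter of consistency, with no change in the number. The defect is confined to a supplementary analysis: a reader should not infer that the sensitivity, specificity or predictive values in section 7.1 are compromised, because none of them depends on item 8.

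A patient-level version is feasible but imprecise. The half-width is about 0.11 to 0.12 around an AUC of 0.75, resting on the assumed N20 sensitivity of 40-60% and on N20 being present in every good-outcome patient. For the ratio it is about 0.17 to 0.21, resting on the plan's 90% sensitivity and 75% poor outcome, and on all 28 good-outcome patients having both potentials. The AUC of 0.75 is illustrative throughout. The point is worth correcting before data are merged.

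**What to change.** Replace the second sentence of item 8, and add a matching paragraph to section 7.1, with an analysis labelled exploratory:

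- **Population:** patients with N20 present (at least 0.5 microvolts) on at least one side.
- **Analysis:** relate CPC 3-5 versus 1-2 to N20 amplitude and, separately, to P25/30 amplitude by logistic regression. Report each AUC with a 95% confidence interval.
- **Absent P25/30:** keep these patients in, either through a rank-based AUC with absent as the lowest value or through a presence indicator. Do not use log amplitude.
- **Two sides:** state one rule for combining left and right amplitudes.
- **Ratio:** report it descriptively, only in patients with both potentials present.
- **Label:** call P(good | N20 present) the negative predictive value of absent N20 for poor outcome, as in sections 2 and 7.1.

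The cost is protocol or SAP wording and a small amount of extra analysis. Item 8 already requires the amplitudes and CPC is already recorded, so no new data are needed.

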During the conduction of the study the patient's confidentiality and the unbiased analysis / interpretation of the SSEP recordings of the patients will be continuously ensured by the fact that once enrolled in the study their personal data will be replaced by a study number that will be representative of them. Only the members of the team that collect the data and do not take part in any interpretation of the results of the SSEPs and are not involved as clinicians in the clinical care of the patient will be aware about the correspondence between the study number and the personal and clinical details of each patient. The members of the study team that will be SSEP interpreters will be blinded for any clinical and personal data of the patients and the clinical ICU team will be not aware about the result of the P25/30 study interpretation.

After the SSEP recording has been conducted, between 24 and 36 hours post ROSC, the patients will be followed up by members of the study team. Those members of the team will assess the patients, by CPC and by performing full neurologic clinical examination, on the day of ICU discharge and on the

day of their discharge from Derriford Hospital. The online system SALUS of Derriford hospital will be used to follow up the patients after their discharge from ICU and before their discharge from the hospital.

The study team has already worked collaboratively with the IT and SALUS teams members and they have developed an effective way of patients follow up for the study purposes.

Through SALUS system, the members of the study team responsible for the patients follow up will be notified for the planned patients' discharge date in order the patients to be assessed by a study team member before they leave the hospital. The neurologic outcome, assessed with the Cerebral Performance Category [see figure 1 on the Appendix], will be recorded on the day of Hospital discharge [within the last 24 hours before discharge].

If a study participant died on ICU as a result of severe brain dysfunction or after the decision of ICU Consultant to be withdrawn from invasive organ support due to extremely poor prognosis and futility of further continuation of treatment, then, the discharge CPC would be the most recently recorded, after the patient have remained consistently off sedation [for a period of time varied for different sedatives or combination of sedatives].

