Specifically, in a case that the ICU Consultant in charge considered withdrawing the invasive organ support in one of the study participants due to extremely poor prognosis, then the ICU consultant should notify the ICU research nurse in order one member of the team to perform the CPC score recording. The assessment by CPC must always take place before the decision for withdrawal of treatment is implemented and strictly before the palliative pathway is initiated. If the study team members failed to be notified by the ICU consultant about the withdrawal of treatment and the Palliative pathway is initiated before patient's CPC and neurologic examination recorded then the patient will be excluded from the study.

If a participant died unexpectedly from another cause rather than severe brain dysfunction and / or withdrawal of invasive organ support, then the most recent CPC before death [if possible to be recorded] will be based on the last available clinical assessment off sedation and will be considered as indicative of neurologic outcome for the patients. In case the CPC could not be assessed, the patient would be excluded from the study analysis.

If patients die on ICU while still on sedation and before being possible to assess their CPC then they will be excluded from the study analysis as the assessment of their outcome based on CPC will not be possible.

The Results of the CPC assessment and the outcome of the patients will be stored in the general study databank for further analysis.

The members of the study team with the help of the Derriford Hospital IT team have already created a study team folder on the hospital computer system. Rights to access the study folder have been

provided by Derriford hospital IT only and strictly to the study team members. The access to the folder is password protected. Each member of the study team must protect the patients' confidentiality and treat the data safely as per Good Clinical Practice and Research Governance Principles.

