indicative of neurologic outcome for the patients. In case the CPC could not be assessed, the patient would be excluded from the study analysis.

If patients die on ICU while still on sedation and before being possible to assess their CPC then they will be excluded from the study analysis as the assessment of their outcome based on CPC will not be possible.

The end of the study for each of the patients-participants will be either the discharge from hospital or their death at any time after the SSEP recording.

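### Participants with an interpretable SSEP who die or start palliation without a recorded CPC are excluded, although the protocol's own scale makes death a poor outcome

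*Combined protocol and SAP*

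**What the plan says.** Section 4.1 (Recruitment and conduction of the study) sets three exclusions, and section 6 (Assessment and follow-up) repeats them:

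- **(a) Palliation without a CPC.** The consultant should notify the research nurse before support is withdrawn, so that a CPC can be recorded. If that does not happen and palliation begins before the CPC and "neurologic examination recorded then the patient will be excluded from the study".
- **(b) Unexpected death from another cause.** The last off-sedation CPC is used if there is one. "In case the CPC could not be assessed, the patient would be excluded from the study analysis".
- **(c) ICU death under sedation.** In section 6: "If patients die on ICU while still on sedation and before being possible to assess their CPC then they will be excluded". The reason in both sections is that such patients are "excluded from the study analysis as the assessment of their outcome based on CPC will not be possible".

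Two carry-forward rules cover deaths that do have a CPC. After death from brain dysfunction or withdrawal of support, "the discharge CPC would be the most recently recorded". After an unexpected death from another cause, the last CPC "will be considered as indicative of neurologic outcome for the patients".

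Other parts of the plan bear on this. Appendix Figure 1 lists death as CPC 5, under the poor outcomes, and section 7.1 groups 3 to 5 as poor. Section 6 ends each participant's study at "either the discharge from hospital or their death at any time after the SSEP recording". Section 4.5 withdraws deaths in the first 24 hours separately. Section 7.5 restricts analyses to complete data, while section 7.7 says that everyone eligible is analysed. Date of death is item 12 of the data list in section 4.1, and section 3.1 makes mortality a secondary endpoint.

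**The concern.** What triggers exclusion is dying or starting palliation. A participant discharged alive with CPC 1 or 2 would not ordinarily be removed by any of the three rules. For participants whose SSEP can be read, inclusion therefore depends on the outcome that the test is meant to predict.

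Sensitivity and NPV for poor outcome are primary-objective measures in section 2, and secondary objective 2 asks whether P25/30 beats N20 on exactly these two. Losing poor outcomes at random with respect to the SSEP lowers the proportion with a poor outcome and so raises NPV. If the loss is related to the SSEP, sensitivity and the comparison with N20 are biased as well. Nothing planned would show the effect: section 7.5 summarises missing data and then analyses complete data.

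**Working it through.** **1. The texts side by side.** The reason given for (c) is that a CPC-based outcome cannot be obtained. Figure 1 assigns a CPC to death, and section 7.1 places it in the poor class. Section 6 treats death after the SSEP as the end of follow-up, not as loss to follow-up. The two positions contradict each other. The exclusions also conflict with section 7.7.

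**2. How the timetable produces (c).** Section 4.1 places the SSEP at 24 to 36 hours after ROSC and routine sedation over the first 36 hours. If both clocks start at ROSC, a death between the recording and the end of routine sedation cannot have an off-sedation CPC. That window is at most 36 − 24 = 12 hours.

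**3. The plan's own figure.** Section 7(a) states a minimum of 115, from sensitivity 90%, margin 5 points, 95% confidence, prevalence of poor outcome 75% and a 3% allowance. The usual precision formula gives 1.96² × 0.9 × 0.1 / 0.05² = 138.3 poor outcomes; 138.3 / 0.75 = 184.4; 184.4 / 0.97 = 190.1, or 191 rounded up. The 115 is not reproduced. That is a separate matter; 115 is used below only to set the size of the cohort.

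**4. Inputs for the illustration.**

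- Analysable: 115 × 0.97 = 111.6, taken as 112. Poor: 112 × 0.75 = 84. Good: 28.
- Sensitivity 90% (section 7(a)). A positive test is absent P25/30.
- Specificity 100%, an assumption. Section 1.1 reports that in the cited retrospective study all patients with absent P25/30 did poorly.
- Number of poor outcomes excluded, k, an assumption: 3 (about the whole allowance, 115 × 0.03 = 3.45) or 8 (about 10% of 84).

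**5. Exclusion unrelated to the SSEP.** With n = 84 − k, prevalence = n/(n + 28) and NPV = 28/(28 + 0.1n).

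| k | Prevalence of poor outcome | NPV |
|---|---|---|
| 0 | 84/112 = 75.0% | 28/36.4 = 76.9% |
| 3 | 81/109 = 74.3% | 28/36.1 = 77.6% |
| 8 | 76/104 = 73.1% | 28/35.6 = 78.7% |

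**6. Exclusion related to the SSEP.** Suppose 90% sensitivity is observed in those kept. The value in all 84 lies between 0.9n/84 (all excluded had P25/30 present) and (0.9n + k)/84 (all absent).

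- k = 3: 72.9/84 = 86.8% to 75.9/84 = 90.4%.
- k = 8: 68.4/84 = 81.4% to 76.4/84 = 91.0%.

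**7. Direction.** Now suppose the true sensitivity in all 84 is 90% (75.6 true positives, 8.4 false negatives) and k = 8.

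- Half of those excluded had absent P25/30: observed sensitivity (75.6 − 4)/76 = 94.2%; NPV 28/(28 + 4.4) = 86.4%.
- All had absent P25/30: observed sensitivity (75.6 − 8)/76 = 88.9%; NPV 28/(28 + 8.4) = 76.9%.

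The error in sensitivity can go either way. No N20 figure is given because the documents state no N20 sensitivity.

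**The case against.** The endpoint is neurologic outcome, and the carry-forward rules consistently look for the patient's neurological state before death. On that aim, leaving out someone whose state was never seen off sedation has some logic, and scoring a non-neurological death with P25/30 present as a false negative would penalise the test for something it does not claim to predict. This stands in part for (b), which is to some extent a choice of outcome definition. It does not rescue (a), where support is withdrawn because the outlook is judged very poor and the exclusion follows from a missed notification. Nor does it rescue the reason given for (c), which the protocol's own scale contradicts.

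Rule (a) is a fallback, since notification and a CPC before withdrawal are required. Rule (c) does not say that the SSEP had been done, and a death before recording has no index test and belongs outside the analysis. Both points stand and limit the numbers.

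The movement in NPV is small beside its sampling error: the 95% half-width at 28/36.4 is 1.96 × √(0.769 × 0.231/36.4), about 14 points. This also stands, but sampling error is reported with the estimate, whereas this bias would go unseen.

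A reader might infer that the 3% allowance is the only slack. Section 3 plans 120 patients, which leaves 120 − 112 = 8 over the 112 analysable. That gives some margin in numbers but does not remove selection.

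**Conclusion.** The concern holds for participants with an interpretable SSEP. Rules (a) and (c) are errors against the protocol's own scale; (b) is partly a matter of definition that the plan should settle. The textual conflict is certain. The size of the bias is not: the documents give no count, it may be few, and the figures for 3 or 8 exclusions rest on assumed numbers and an assumed specificity. It should be fixed before the databanks are merged.

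Three stronger readings are tempting but not supported:

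- **That the rules flatter P25/30.** Losing non-neurological deaths with P25/30 present would raise sensitivity. Losing patients palliated early after a disclosed absent N20 could lose true positives and lower it. The documents do not settle which dominates.
- **That deaths are certainly lost from the mortality endpoint.** Rule (a) excludes from the study, and (b) and (c) from the analysis, so a literal reading removes them. But section 7.7 can be read the other way, and the reason given for (c) concerns only CPC.
- **That carrying forward the last CPC is itself a mistake.** The protocol gives a brief rationale, that this CPC indicates neurologic outcome. After brain dysfunction or withdrawal, a last CPC of 3 or 4 is already poor, so the binary endpoint does not change.

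**What to change.** - **Sections 4.1 and 6.** Delete the three exclusions for participants with an interpretable SSEP. Deaths before the recording stay out.
- **Primary analysis.** Code every in-hospital death without a recorded off-sedation CPC as CPC 5 (poor), whatever the cause. A palliated participant who leaves hospital alive keeps the discharge CPC. Deaths with a recorded CPC follow the carry-forward rules as written.
- **Sensitivity analyses.** Report (i) all in-hospital deaths as CPC 5 and (ii) deaths without a CPC left out. Give the number left out by P25/30 and N20 status, and show sensitivity, NPV and the N20 comparison each way.
- **Section 3.1.** State that all deaths count for mortality.
- **Sections 7.5 and 7.7.** Reconcile them so that a death without a CPC is not treated as missing data.

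The cost is wording and two extra analyses. Date of death is already collected, coding deaths without a CPC needs no ruling on cause, and no test or aspect of care changes.

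There are two drawbacks. Some non-neurological deaths will count as poor. And because clinicians see the N20 result (sections 4.1 and 5), which may inform withdrawal, coding deaths after withdrawal as poor may favour N20 in the comparison. Reporting results with and without these deaths lets the reader see both effects.

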3.1 STUDY OUTCOME MEASURES

Primary Endpoint: Neurologic outcome assessed by Cerebral Performance Category [CPC] score at hospital discharge.

Secondary endpoints: Mortality at hospital discharge and at 28 days [which occurs first], comparison of prognostic benefit of N20 and P25/30 SSEPs-based multimodal prognostic models.

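### The primary endpoint scores death as CPC 5 (poor), but no written death rule assigns CPC 5, so an in-hospital death after a last CPC of 1-2 is analysed as a good outcome

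*Combined protocol and SAP*

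**What the plan says.** Section 7.1 states: "The primary outcome measure is the CPC score at hospital discharge with discrete values ranging from 1 to 5". It continues: "The score will be dichotomised as 1-2 (positive or good outcome) and 3-5 (negative or poor outcome"). Section 3.1 gives the same endpoint and time point. Appendix Figure 1 lists death as category 5, under the poor outcomes.

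Section 4.1, repeated in section 6, then sets rules for participants who die:

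- **ICU death from brain injury or after withdrawal of support.** The rule opens "If a study participant died on ICU as a result of severe brain dysfunction or after the decision of ICU Consultant" and concludes that "the discharge CPC would be the most recently recorded, after the patient have remained consistently off sedation". If palliation starts before the study team has recorded a CPC, the patient is excluded.
- **Unexpected death from another cause.** The trigger is "If a participant died unexpectedly from another cause rather than severe brain dysfunction and / or withdrawal of invasive organ support", with no location given. In that case "the most recent CPC before death [if possible to be recorded] will be based on the last available clinical assessment off sedation", and this value stands as the neurological outcome. If no CPC could be assessed, the patient is excluded.
- **ICU death under sedation before CPC could be assessed.** The patient is excluded.

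Section 6 ends each patient's follow-up at hospital discharge or at death after the recording. Mortality is a separate secondary endpoint.

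**The concern.** The endpoint as defined and the endpoint as it would be scored are different variables. One treats death as the worst category. The other records the last neurological state before death and drops deaths for which none was recorded. Nothing converts the carried-forward score to 5, and no analysis is planned that scores death as 5.

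This bears on the quantities the study exists to estimate. Section 2 makes sensitivity, specificity and predictive values of P25/30 a primary objective, and a secondary objective is to show higher sensitivity and negative predictive value (NPV) than N20. A patient with P25/30 present who recovers to CPC 1-2 and then dies is a correct negative under the death rules and a missed poor outcome under the printed scale. If the choice is left open, it can be made after the results are known.

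There is also a gap. The neurological and withdrawal rule and the sedation rule are both confined to ICU, while follow-up runs to hospital discharge.

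**Working it through.** **1. Which rule covers which death**

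| Death before hospital discharge | ICU | Ward |
|---|---|---|
| Severe brain dysfunction, or after withdrawal of support | last recorded CPC off sedation; excluded if palliation began before a CPC was recorded | no rule |
| Unexpected, another cause | last CPC off sedation, or excluded | same rule, since no location is named |
| Under sedation, CPC not assessable | excluded | not named |
| Expected, another cause, no withdrawal | no rule unless under sedation and unassessed | no rule |

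No cell gives CPC 5. Most neurological deaths would probably stay poor through a last CPC of 3 or 4. The cell that can change the analysis in a patient's favour is a death after a last CPC of 1-2.

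**2. The plan's own figure**

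The only calculated figure is the sample size of 115 (section 7, number of participants). The standard precision formula with the stated inputs gives 1.96² × 0.90 × 0.10 / 0.05² = 138.3 poor outcomes; 138.3 / 0.75 = 184.4; 184.4 / 0.97 = 190.1, so 191. I could not reproduce 115. That is a separate matter and this point does not depend on it. I use 115 only to set the scale.

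**3. Illustration of size**

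Inputs from the plan: 115 patients, 3% loss, 75% poor outcome, 90% sensitivity, 5-point margin.

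- Analysed: 115 × 0.97 = 111.6, taken as 112.
- Poor under the death rules: 0.75 × 112 = 84. Good: 112 − 84 = 28.
- Detected: 0.90 × 84 = 75.6, taken as 76. Missed: 84 − 76 = 8.

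Assumptions not in the documents: k of the 28 patients counted as good died in hospital, and all k had P25/30 present. For NPV I also assume that every patient with a good outcome had P25/30 present, as section 1.1 reports for the cited retrospective study.

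With death scored 5, sensitivity = 76 / (84 + k) and NPV = (28 − k) / 36, where 36 = 28 + 8.

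| k | Sensitivity | Fall (points) | NPV |
|---|---|---|---|
| 0 | 76/84 = 90.5% | 0 | 28/36 = 77.8% |
| 1 | 76/85 = 89.4% | 1.1 | 27/36 = 75.0% |
| 2 | 76/86 = 88.4% | 2.1 | 26/36 = 72.2% |
| 4 | 76/88 = 86.4% | 4.1 | 24/36 = 66.7% |
| 5 | 76/89 = 85.4% | 5.1 | 23/36 = 63.9% |
| 6 | 76/90 = 84.4% | 6.0 | 22/36 = 61.1% |

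**4. Does the starting point matter?**

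The plan does not say which scoring lies behind the 75%. If 84 is instead the count with death scored 5, and sensitivity is 90% in the other 84 − k, the printed-scale sensitivity is 0.9 × (84 − k) / 84. This gives 85.7% at k = 4 and 83.6% at k = 6, against 90.0%. The fall exceeds 5 points when 0.9k / 84 > 0.05, that is k > 4.7, so again at five.

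**5. Comparison with N20**

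If the k patients also have N20 present (assumption), both sensitivities are multiplied by 84 / (84 + k). At k = 6 this is 84/90 = 0.93. The difference between the tests shrinks by about 7% of its size and keeps its sign. It moves more only if the two potentials disagree in these patients.

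**The case against.** Carrying the last CPC forward looks deliberate. The study asks about neurological prognosis, and calling a neurologically recovered patient who dies of something else a poor neurological outcome adds noise to a test of brain function. The rule is stated prospectively. That stands: last-CPC scoring is defensible, and choosing between the scorings is partly a trade-off. It does not remove the need for the endpoint, the scale and the rule to agree.

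It is also fair that the number of affected patients may be zero or one, and that ward deaths are not all uncovered: an unexpected other-cause ward death falls under the rule as worded, and CPC at ICU discharge is scheduled, so an earlier value should exist.

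A reader might draw three stronger inferences, which the documents do not support:

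- **That a cause-of-death judgement by clinicians who know the N20 result decides good or poor.** N20 is disclosed to the ICU team, but both rules carry the last CPC forward, so for an assessed ICU death the cause label does not change the score. Study team members assess CPC, and no section says who judges cause of death.
- **That the assumed 75% poor outcome is built on the 70% local mortality in section 1.1.** Section 7 attributes the 75% to team experience and pilot data and does not link the two.
- **That the rule contradicts the mortality endpoint.** A patient can have a last CPC of 2 and still be counted as a death there; the endpoints measure different things.

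**Conclusion.** The conflict is on the face of the text. The endpoint includes death as CPC 5, poor; the death rules assign the last off-sedation CPC or exclude the patient; and certain ward deaths have no rule. An in-hospital death after a last CPC of 1-2 is therefore analysed as good.

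The size is unknown. In the illustration each affected patient with P25/30 present costs about 1 point of sensitivity and just under 3 points of NPV (1/36 = 2.8). About five such patients are needed to pass the planned 5-point margin; fewer stay within it. This rests on an assumed count and on all affected patients having P25/30 present. An affected patient with P25/30 absent would move the other way, from false positive to true positive. The effect of adding back excluded deaths is not included and cannot be computed from the documents. The point should be settled before analysis, but it does not show that the study's comparison of P25/30 with N20 would be reversed.

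**What to change.** Reconcile the death rules in sections 4.1 and 6 with section 7.1 and Appendix Figure 1, and prespecify two scorings for patients with an SSEP recording who remain in the study:

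- **(a)** the scale as printed: any death before hospital discharge, in any location and from any cause, is CPC 5;
- **(b)** the last off-sedation CPC, with wording extended to the ward deaths that now have no rule.

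Name which is primary before the databanks are merged; (a) matches the endpoint as stated. Report sensitivity, specificity and predictive values under both, side by side, for P25/30 and N20. State that (a) also brings in deaths now excluded for lack of a CPC, and report how many there are and their P25/30 and N20 results.

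Date of death is already on the data collection list in section 4.1, and section 7.6 allows a separate SAP before completion. The cost is wording, one extra table, a different analysis set under (a), and possibly a lower reported sensitivity because some deaths are not brain-related. Showing (b) beside it lets the reader judge that.
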